7.9 Concomitant Medications and Treatments

Information on all medications taken within 4 weeks prior to initiation of study treatment and all concomitant medications taken during the study, as well as the drug indications, will be recorded in the electronic case report form (eCRF). During the 28-day follow-up period after permanent discontinuation of HS-10296, all concomitant medications, including anti-tumor therapy, will be recorded in the eCRF, and only anti-tumor therapy will be recorded thereafter. Patients taking conventional medications should continue to use such medications throughout the study if medically feasible. Other anti-tumor agents, investigational products, and radiation therapy should not be administered when a patient is on study treatment and donated drugs unless the patient must receive radiation therapy to manage the pain caused by bone metastases. The pleural effusion drainage for the purpose of symptom control should be permitted in the absence of objective disease progression as assessed by radiographic assessment when a patient is on study treatment; anti-tumor agents are not allowed in the management of pleural effusion; and the investigator should re-assess the presence or absence of disease progression of this non-target lesion and overall disease progression depending on the volume and nature of the pleural

effusion after completion of pleural effusion drainage. The above information should be recorded in detail in the original medical record.

Prophylaxis for diarrhea, nausea, and vomiting should not be given prior to the first dose of study drug, but prophylaxis is allowed after the first dose. Patients are allowed to receive blood transfusions at any time during the study.

Granulocyte colony stimulating factors should not be used prophylactically during treatment for Cycle 1. Use of prophylactic colony stimulating factors may be considered after Cycle 1 following discussion with the Sponsor's physician.

Patients can receive treatment with corticosteroids and/or bisphosphonates or denosumab for bone metastases.

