9.1.3.2 Safety Follow-up (28-day follow-up)

Safety follow-up refers to the visit procedures that a subject should complete 28 days after discontinuation of study treatment (discontinuation of the investigational product). During the visit, information on newly emerged AEs or follow-up of AEs experienced at the time of discontinuation, and all concomitant medications (including anti-tumor therapy) will be collected by telephoning the patient. The follow-up should be performed until the SAE has an outcome, if possible. It includes the following items:

- Record adverse events (newly emerged AEs or follow-up of AEs experienced at the time of discontinuation)
- Record concomitant medications (all concomitant medications including anti-tumor therapy)

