9.1.3.3 Progression Follow-up

Progression follow-up refers to the visit procedures to be completed by subjects who discontinue treatment for reasons other than disease progression. RECIST 1.1 assessments will be performed every 6 weeks (C1 to C21) or every 12 weeks (C23 and thereafter) (relative to the date of randomization). Patients who continue treatment after progression due to possible clinical benefit will continue to undergo tumor assessments. It includes the following items:

Progression follow-up for subjects who discontinue treatment for reasons other than disease progression:

- Response evaluations in solid tumors will be performed every 6 weeks (C1 to C21) or every 12 weeks (C23 and thereafter) until disease progression as assessed by the investigator per RECIST 1.1
- ECOG PS score will be performed every 6 weeks (C1 to C21) or every 12 weeks (C23 and thereafter) until disease progression as assessed by the investigator per RECIST 1.1
- Record concomitant medications: only subsequent anti-tumor therapy will be recorded in detail until disease progression
- If a subject has disease progression before the completion of the 28-day safety follow-up, the safety follow-up should be continued until 28 days after discontinuation of treatment

Progression follow-up for subjects who continue study treatment (donated drug) after disease progression:

- It is recommended to perform tumor assessments per RECIST 1.1 every 6 weeks (C1 to C21) or every 12 weeks (C23 and thereafter) until progression after the administration of donated drug as judged by the investigator or discontinuation of treatment before progression (safety reasons or investigator's judgment or subject's decision)
- ECOG PS score will be performed every 6 weeks (C1 to C21) or every 12 weeks (C23 and thereafter) until further progression as judged by the investigator or discontinuation of treatment before progression (safety reasons or investigator's judgment or subject's decision)
- Record concomitant medications: all concomitant medications (including anti-tumor therapy) will be recorded until 28 days after discontinuation of treatment, and only anti-tumor therapy will be collected thereafter
- Record adverse events: for subjects who continue to receive study treatment after progression, AEs and SAEs will be continued collecting until 28 days after discontinuation of treatment, and only AEs with no outcome and study drug-related SAEs will be collected thereafter

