11.1.3 Recording of Adverse Events

11.1.3.1 Time Period for Collecting AEs and SAEs

AEs will be collected throughout the study from informed consent to the end of the safety follow-up period. The safety follow-up period is defined as 28 days after discontinuation of the investigational product.

SAEs occurring throughout the study (from informed consent to the end of the follow-up period) should be reported to the Sponsor by the site within 24 hours of becoming aware of the SAEs.

After discontinuation of HS-10296, SAEs considered related to the investigational product and study procedures should be continued collecting, and the patient's disease progression should be followed. Some patients may remain on medication after the last database lock. For patients who continue receiving HS-10296, the Sponsor will collect only SAEs, as well as information on discontinuation of study treatment due to AEs/SAEs, until 28 days after discontinuation of treatment.

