12.3.3 Safety Analysis

12.3.3.1 Adverse Event

AEs occurring from treatment initiation until 28 days after the last dose will be summarized in the safety evaluation. AEs that occur prior to the initiation of study treatment and those occurring 28 days after the last dose will not be included in the summary table of AEs.

Adverse events occurring post-dose will be summarized by treatment group, mainly including:

- 1) The number and proportion of patients with at least one AE;
- 2) The number and proportion of patients with at least one study drug-related AE;
- 3) The number and proportion of patients with at least one AE of higher severity (CTCAE Grade ≥ 3);
- 4) The number and proportion of patients with at least one study drug-related AE of higher severity (CTCAE Grade ≥ 3);
- 5) The number and proportion of patients with at least one SAE;
- 6) The number and proportion of patients with dose modifications due to AEs;
- 7) The number and proportion of patients who have withdrawn from the study due to AEs;
- 8) The number and proportion of patients who died due to AEs.

Adverse events will be summarized by system organ classes and preferred terms. All adverse events will be tabulated.

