		1	2	3	4	5	6	7-9		28-day follow-up ^b	Progression Follow-up Every 6/12 weeks	Survival Follow-up Every 6 weeks
Treatment cycle ^{c/day}		C1 D1	C1 D8	C1 D15	C2 D1	C3 D1	C4-C6 D1	D1 of C7 and Every 6/12 weeks thereafter	NA	NA	NA	NA
Day	-28	1	8	15	22	43	64-106	127+	NA	NA	NA	NA
Window period (days)	NA	0	±2	±2	±2	±7	±7	±7	+7	NA	±7	±7
Comments	
a. Subjects will be followed every 3 weeks (1 cycle) from Cycles 1 to 6; every 6 weeks (2 cycles) from Cycle 7 onwards; and two additional visits will be added on C1D8 and C1D15.
 
b. Subjects should be followed up by telephone 28 days (± 7 days) after discontinuation of study drug.
 
c. One cycle is defined as 21 days of continuous treatment.
 
d. These assessments at baseline should be completed prior to dosing on the visit day. If screening tests are completed within 7 days prior to the first dose of investigational product, they will not be required to perform on C1D1.
 
e. ECGs may be performed in the event of any cardiac-related AE.
 
f. Baseline tests should be performed within 28 days prior to the first dose. Assessments will be performed every 6 weeks after the start of treatment until disease progression as determined by centralized assessment per RECIST 1.1 criteria, even if the subject discontinues treatment prior to progression or has received other anti-tumor therapies. Tumor assessment data will be obtained from CT or MRI (contrast-enhanced CT or MRI is recommended to be preferred).
 
g. Tumor response results assessed by the investigator will be collected.
 
h. Subjects should be contacted to determine their survival status after the data cutoff date as determined by OS analysis.
											

• Study Plan for HS-10296 Crossover Treatment												
Visit ^a	HS-10296 Pre-crossover Visit	Treatment Period							Study Discontinuation Follow-up	Follow-up Period		
		2	3	4	5	6	7-9	10+		28-Day Follow-up	Progression Follow-up Every 6 weeks	Survival Follow-up Every 6 weeks
Treatment cycle ^b	C0	C1	C1	C1	C2	C3	C4-C6	Every 6 weeks from C7 onwards	NA	NA	NA	NA
Day	-28	D1	D8	D15	D22	D43	D64-106	D127	NA	NA	NA	NA
Window period (days)	NA	0	±2	±2	±2	±7	±7	±7	+7	NA	±7	±7
Informed consent	×											
Collection of tumor/blood samples after disease progression during the randomized treatment phase	×											
T790M mutation test	×											
Tumor assessment	×	The assessment is recommended to perform every 6 weeks ± 7 days per RECIST 1.1									×	

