### 5.1. Adverse events

Adverse events will be coded with MedDRA 23.0 or a higher version.

CTCAE (4.03) will be obtained for the rating of the seriousness of adverse events. AEs that occur from the start of treatment to within 28 days after the last treatment will be summarized in the safety evaluation. AEs occurring prior to treatment initiation and AEs occurring within 28 days after the last treatment are tabulated separately and will not be included in summary tables for AEs.

General principles to follow when summarizing adverse events:

- 1) Adverse events are summarized by treatment group and system organ class/preferred time (SOC/PT).
- 2) If the same subject has the same adverse event multiple times, the one with the highest correlation with the investigational drug will be used to summarize the investigational drug-related AE and the one with the highest severity will be used for the summary of adverse event seriousness.
- 3) Only adverse events during the randomized, double-blind treatment stage and not during the cross-treatment stage are included.

All of the AEs of each subject will be presented in a list.

Related to the investigational drug refers to “definitely related,” “possibly related,” and “unable to be determined.”

Serious adverse events will be summarized and tabulated individually.

The following summary results will be given:

- 1) Summary of all adverse events
- 2) All adverse events summarized by system organ class and preferred term
- 3) Investigational drug-related adverse events summarized by system organ class and preferred term
- 4) All common adverse events summarized by system organ class and preferred term
- 5) All common investigational drug-related adverse events summarized by system organ class and preferred term
- 6) Adverse events of CTCAE grade  $\geq 3$  summarized by system organ class and preferred term
- 7) Investigational drug-related adverse events of CTCAE grade  $\geq 3$  summarized by system organ class and preferred term
- 8) Serious adverse events (SAEs) summarized by system organ class and preferred term
- 9) Investigational drug-related serious adverse events (SAEs) summarized by system organ class and preferred term
- 10) Adverse events leading to permanent discontinuation summarized by system organ class and preferred term
- 11) Investigational drug-related adverse events leading to permanent discontinuation summarized by system organ class and preferred term

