16.2.7 Lists of adverse events	List 16.2.7.1 List of all adverse events (during treatment and 28 days after the last medication)-safety set List 16.2.7.2 List of all adverse events (before the first medication)-safety set List 16.2.7.3 List of all adverse events (28 days after the last medication)-safety set List 16.2.7.4 List of all serious adverse events-safety set

List 16.2.7.5 List of adverse events leading to death-safety set
16.2.8 Laboratory tests, ECGs, LVEF, ECOG PS scores, etc.
List 16.2.8.1 List of laboratory test results (routine blood)-safety set
List 16.2.8.2 List of laboratory test results (blood chemistry)-safety set
List 16.2.8.3 List of laboratory tests (routine urine)-safety set
List 16.2.8.4 List of examination results of vital signs (including weight and ECOG PS score)-safety set
List 16.2.8.5 List of physical examination results-safety set
List 16.2.8.6 List of 12-lead ECG examination results-safety set
List 16.2.8.7 List of LVEF test results-safety set
List 16.2.8.8 List of ophthalmological examination results-safety set

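### The ±7-day window in Appendix B note b lets the telephone safety call fall on days 21 to 27, before the 28-day adverse-event period ends; a minor gap that a +7-day window closes

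*Protocol*

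**What the plan says.** **When the call is made.** Protocol Appendix B, note b to the randomized-treatment table: "Subjects should be followed up by telephone 28 days (± 7 days) after discontinuation of study drug". The window row of that table shows NA for the 28-day column, +7 for the discontinuation visit and ±7 for progression and survival follow-up. Section 9.1.3.2 places the contact 28 days after stopping, without a window, and says that the information on new AEs and on concomitant medications "will be collected by telephoning the patient".

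**What period it serves.** Protocol 11.1.3.1 collects AEs to the end of safety follow-up: "The safety follow-up period is defined as 28 days after discontinuation of the investigational product". Concomitant medications are due for the same time (7.9): "During the 28-day follow-up period after permanent discontinuation of HS-10296, all concomitant medications, including anti-tumor therapy, will be recorded". For patients who progress before that follow-up is complete, 9.1.3.3 states that "the safety follow-up should be continued until 28 days after discontinuation of treatment".

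**What is reported.** Protocol 12.3.3.1: "AEs occurring from treatment initiation until 28 days after the last dose will be summarized in the safety evaluation". SAP 5.1: "AEs that occur from the start of treatment to within 28 days after the last treatment will be summarized in the safety evaluation". SAP List 16.2.7.1 is titled "List of all adverse events (during treatment and 28 days after the last medication)-safety set". Protocol 12.2 and SAP 5.1 each also contain a sentence that tabulates AEs from the 28 days after treatment separately and keeps them out of the summary tables.

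**The concern.** The duty to collect AEs runs to day 28, but the one scheduled contact that asks about new AEs after treatment may take place on day 21. Nothing requires a second contact when the call is early. An AE that starts on day 25, after a call on day 21, has not been recorded, so rules on following up known events do not reach it.

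At stake is the completeness of late AE reporting. Comparing safety between the arms is a secondary objective, and the listing of AEs to 28 days after the last dose would imply a coverage that the schedule does not guarantee. The three statements on timing (±7 in note b, NA in the window row, no window in 9.1.3.2) also leave sites to choose which one applies.

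**Working it through.** **1. The call window.** Inputs from note b: target day 28, tolerance 7 days.
- Earliest call: 28 − 7 = day 21. Latest call: 28 + 7 = day 35.
- Permitted days: 35 − 21 + 1 = 15.

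**2. Days left uncovered.** The period ends on day 28 (11.1.3.1). Uncovered days = 28 − call day, or zero for a call on day 28 or later.
- Day 21: 28 − 21 = 7 days, and 7/28 = 25% of the period.
- Day 27: 28 − 27 = 1 day, and 1/28 = 3.6%.
- Days 28 to 35: none.

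**3. Share of the whole AE window.** This window runs from first dose to 28 days after the last. The documents give no expected treatment duration, so I assume 10 to 15 months, taking the design median PFS values as a stand-in. SAP 2.2 sets one month at 30.4375 days.

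| Time on treatment | AE window | 1 day uncovered | 7 days uncovered |
|---|---|---|---|
| 10 months | 304.4 + 28 = 332.4 days | 1/332.4 = 0.30% | 7/332.4 = 2.1% |
| 15 months | 456.6 + 28 = 484.6 days | 1/484.6 = 0.21% | 7/484.6 = 1.4% |

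The range is 0.2% to 2.1%, for patients called early only.

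**4. Average over all patients.** The share called early is not in the documents. If calls were spread evenly over the 15 permitted days (an assumption), the mean uncovered time would be (7 + 6 + 5 + 4 + 3 + 2 + 1)/15 = 28/15 = 1.9 days. That is 1.9/484.6 = 0.4% to 1.9/332.4 = 0.6% of the AE window. Calls clustered near day 28 would lose less.

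**5. What later contacts collect.**
- Progression follow-up after stopping treatment (9.1.3.3) lists tumor assessment, ECOG score and subsequent anti-tumor therapy.
- Survival follow-up (9.1.3.4) collects AEs that are still unresolved.
- Serious AEs related to the drug or to study procedures continue to be collected (11.1.3.1), and clinically significant abnormalities are followed to recovery or stabilization (7.11, item 2).
- Patients preparing for crossover have AEs recorded at the pre-crossover assessment (9.2.2.1).

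This leaves new non-serious AEs, and unrelated serious AEs the site does not learn of, with onset between an early call and day 28.

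**6. The Appendix B cell.** The table also has a cell, by the follow-up columns, for items arising before the 28-day follow-up is complete. In the text of the table it stands on the concomitant-medication line, and the AE line shows only an arrow. If the cell covers both rows and completion means day 28, later contacts would pick up these AEs. If it covers medications only, they would not.

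**The case against.** The best case on the other side is that the gap is already closed. Sections 11.1.3.1 and 9.1.3.3 both tie the end of safety follow-up to day 28, so completion in the Appendix B cell most naturally means day 28 and not the date of the call. On that reading later contacts record what arose up to day 28. Note b schedules a call and does not shorten the duty to collect. Section 4.3.1 also names diaries, telephone and in-hospital follow-up as routes for AEs outside the hospital.

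Much of this stands. For concomitant medications the cell probably does the work. For AEs it may, but the table text does not show that it spans the AE row. Section 4.3.1 is a general statement on risk control and schedules no contact after treatment ends.

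Little drug remains in plasma by day 21 (504 hours). With half-lives of 30.7 to 37.5 hours for HS-10296 and 50 to 70 hours for its metabolite (4.2.4), that is at least 504/70 = 7.2 half-lives. Section 6.1 equates five gefitinib half-lives with 10 days, so day 21 is about 10.5. This limits the likely number of late drug effects, although plasma levels say nothing about how long irreversible target effects persist.

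A reader might infer that AEs after an early call are lost outright, or that the safety comparison is biased. The documents support neither. Several routes still capture events, the collection duty stays at day 28, and the call rule is the same in both arms.

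**Conclusion.** Note b permits a call that ends active questioning 1 to 7 days early, and it disagrees with the window row and with 9.1.3.2. Late new non-serious AEs, and unrelated serious AEs unknown to the site, may be missed unless the Appendix B cell is read as covering AEs. The point is minor.

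The size for an early-called patient is 0.2% to 2.1% of the AE window, resting on the assumed 10 to 15 months of treatment. The average over all patients depends on call timing, which the documents do not give. PFS is untouched.

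It would also go too far to say that the AE summary tables are understated. Because protocol 12.2 and SAP 5.1 each contain both an inclusion and an exclusion sentence for post-treatment AEs, the loss may reach only the listings.

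**What to change.** Change note b to 28 days (+7 days) and put +7 in the window row of the 28-day column. The table already uses a one-sided +7 for the discontinuation visit. Have the call ask for AEs and concomitant medications with onset up to day 28, so that a later call does not lengthen the period. Earliest call: day 28, with 28 − 28 = 0 days uncovered.

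The cost is a wording amendment and no extra contact. The call window narrows from 15 days to 35 − 28 + 1 = 8, so missed windows become more likely. Some calls will also fall after new therapy has started, or during crossover dosing, which may begin after a 10-day gefitinib washout. The onset date and any new therapy must therefore be recorded so that these AEs are attributed correctly: protocol 12.2 flags AEs after further anti-tumor therapy, and SAP 5.1 leaves crossover-stage AEs out of the summaries.

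An alternative is to keep ±7 and state that AEs to day 28 are recorded whatever the call date. That keeps the wider window, but patients called early would then need either a second contact or an explicit AE question at a later one.
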